2. TRIAL OBJECTIVES AND ENDPOINTS

Objectives and Endpoints:		
	Objectives	Endpoints
Part 1: Dose Optimization		
Primary	To identify a clinically active and tolerable systemic exposure range of bezuclastinib in subjects with AdvSM	
 Safety assessments (incidence of adverse events [AEs], serious adverse events [SAEs], changes from baseline in laboratory results) and dose modifications Pharmacokinetics (PK) and pharmacodynamic assessments Overall response rate (ORR) based on the modified IWG-MRT-ECNM response criteria per Central Response Review Committee (CRRC)
Part 2 Stage 1: Dose Confirmation		
Primary	To confirm the optimal dose of bezuclastinib in subjects with AdvSM	
 Safety assessments (incidence of AEs, SAEs, changes from baseline in laboratory results) and dose modifications PK and pharmacodynamic assessments ORR based on the modified IWG-MRT-ECNM response criteria per Central Response Review Committee (CRRC)
Part 2 Stage 2: Expansion		
Primary	To determine the efficacy of bezuclastinib at the selected optimal dose in subjects with AdvSM who are evaluable based on the modified IWG-MRT-ECNM response criteria	ORR defined as the percentage of subjects classified as confirmed responders (complete response [CR], CR with incomplete hematologic recovery [CRh], partial response [PR], and clinical improvement [CI]) according to modified IWG-MRT-ECNM response criteria as assessed by CRRC
Part 1 and Part 2		
Secondary	To characterize the safety and tolerability of bezuclastinib in subjects with AdvSM	Incidence of AEs, SAEs, AEs leading to dose modifications, and changes from baseline in laboratory results
	To evaluate additional efficacy parameters with bezuclastinib in subjects with AdvSM	Duration of response (DOR), defined as the date of the first documented response (CR, CRh, PR, or CI) to date of first documented disease progression or loss of response, or death from any cause, whichever occurs first, based on modified IWG-MRT-ECNM response criteria
		Time to response (TTR), defined as the date of randomization/first dose of study drug to the date of the first documented response (CR, CRh, PR, or CI) based on modified IWG-MRT-ECNM response criteria
		Progression-free survival (PFS), defined as the date of randomization/first dose of study drug to the date

Objectives and Endpoints:		
	Objectives	Endpoints

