8.2. DETERMINATION OF SAMPLE SIZE

Approximately 28 subjects will be randomized 1:1:1:1 into 4 dose cohorts (Formulation A) in Part 1, including up to 4 subjects who are non-evaluable per modified IWG-MRT-ECNM response criteria based on lack of evaluable organ damage per modified IWG-MRT-ECNM criteria. It was determined that approximately 6 subjects evaluable per modified IWG-MRT-ECNM response criteria per group (24 total) would allow for ruling out an ORR of 60% or higher if a dose group had an ORR estimate of 16.7% or less (ie, if the ORR for a dose is 1/6, the upper bound of the 1-sided 90% confidence interval is 51.0% via a Clopper-Pearson exact confidence interval). Dose decisions will be based on an assessment of safety, biomarker, and clinical efficacy, and PK endpoints at each dose, with summary statistics and figures being used to illustrate dose-response.

Part 2 of the study will enroll approximately 75 subjects who are evaluable per modified IWG-MRT-ECNM criteria and up to an additional 15 subjects with AdvSM who are non-evaluable per modified IWG-MRT-ECNM response criteria at study entry.

For Part 2 Stage 1, approximately 20 subjects who are evaluable per modified IWG-MRT-ECNM will be randomized in a 1:1 ratio to receive bezuclastinib 150 mg QD or 300 mg QD (Formulation B). It was determined that approximately 10 subjects evaluable per modified IWG-MRT-ECNM response criteria per group would allow for ruling out an ORR of 60% or higher if a dose group had an ORR estimate of 30.0% or less (ie, if the ORR for a dose is 3/10, the upper bound of the 1-sided 90% confidence interval is 55.2% via a Clopper-Pearson exact confidence interval). The determination of the optimal dose will be based on totality of the data including assessment of safety, biomarker and clinical efficacy, and PK endpoints at each dose level.

For Part 2 Stage 2, approximately 55 subjects who are evaluable per modified IWG-MRT-ECNM response criteria will be enrolled. The null hypothesis is that ORR for subjects who received bezuclastinib treatment will be the same as the historical control (28%) (RYDAPT SmPC, 2021). Assuming the ORR for subjects who received bezuclastinib is 60%, 55 evaluable subjects will provide at least 90% power to reject the null hypothesis based on a Chi square test at one-sided alpha of 0.025.

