For the following endpoints, PFS and OS will be summarized using Kaplan-Meier Product-Limit survival analysis, including the estimates of 25%, 50%, and 75% percentiles and 95% confidence intervals, and DOR and TTR will be summarized with mean and standard error (if data warrant):

- DOR, defined as the time from the date of first CR, CRh, PR, or CI to the date of disease progression or death from any cause, whichever occurs first. DOR can only be determined in subjects who have CR, CRh, PR, or CI.

- TTR, defined as the time from the date of randomization/first dose of study drug until the first documented response (CR, CRh, PR, or CI). Time to best response will also be calculated.
- PFS, defined as the date of randomization/first dose of study drug to the date of first documented confirmed disease progression or death from any cause, whichever occurs first.
- OS, defined as the date of randomization/first dose of study drug to the date of death from any cause.

The following censoring rules will apply to subjects who survive at the end of the study:

- All subjects will be censored at the last date of study participation.
- Subjects who are lost to follow-up and subjects who discontinued study for any reason will be censored at the last date of contact.

An assessment of OS and PFS will be performed with and without censoring for subsequent therapy.

Changes in spleen and liver sizes will be assessed by MRI and palpation.

Evaluation of biomarkers of mutation burden and VAF in bone marrow or other samples as appropriate before and after treatment with bezuclastinib ex vivo. Potential biomarkers will be correlated with clinical outcomes.

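### Duration of response is right-censored, but Section 8.7 summarizes it by mean and standard error instead of Kaplan-Meier, so the figure tracks follow-up more than durability

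*Protocol*

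**What the plan says.** Protocol Section 8.7 divides four time endpoints between two methods in a single sentence. For two of them, "PFS and OS will be summarized using Kaplan-Meier Product-Limit survival analysis", with quartile estimates and 95% confidence intervals. For the other two, "DOR and TTR will be summarized with mean and standard error (if data warrant". No alternative is named for the case where the data do not warrant it.

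The same section defines the endpoint: "DOR, defined as the time from the date of first CR, CRh, PR, or CI to the date of disease progression or death from any" (the quote breaks off there; deaths of every kind count). It adds that "DOR can only be determined in subjects who have CR, CRh, PR, or CI". Section 2 uses a wider end event, running "to date of first documented disease progression or loss of response, or death from any cause, whichever occurs first".

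Two censoring rules follow, for subjects alive at the end of the study: "All subjects will be censored at the last date of study participation", and "Subjects who are lost to follow-up and subjects who discontinued study for any reason will be censored at the last date of contact".

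The synopsis, Section 2 and the rest of Section 8 give DOR no Kaplan-Meier estimate, median or landmark rate. The protocol names the method itself, so this is not a detail left open for the SAP.

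**The concern.** DOR ends in an event: progression or death, plus loss of response under Section 2. A responder who has had no such event by the cutoff contributes only a lower bound. A mean can handle that lower bound in two ways. It can treat it as the finished duration, which is too short. Or it can leave the responder out, which keeps only the responses that failed early. Either way the mean is too low, and the standard error describes the precision of the wrong quantity.

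Censoring should be expected. Treatment continues until progression, toxicity or another listed reason. Table 3 schedules no response assessment after end of treatment, so a responder who stops for another reason may never have an observed end of response. Section 8.4.4 also foresees analyses at a cutoff when some subjects have been followed for little more than 20 weeks.

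Part 2 Stage 2 is a single arm tested against a historical rate of 28%, and its responder definition includes clinical improvement. Whether those responses last is a large part of how the response rate will be read, and the planned statistic cannot show it reliably.

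**Working it through.** The protocol states no DOR figure, so there is nothing of its own to reproduce. The check asks what the planned mean would report under known durability.

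**Inputs from the protocol.** Section 8.2: "Assuming the ORR for subjects who received bezuclastinib is 60%, 55 evaluable subjects will provide at least 90% power". This implies about 0.60 × 55 = 33 responders in Part 2 Stage 2.

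**Assumptions, not in the protocol.** DOR is exponential with median m, so λ = ln 2 / m and the true mean is 1/λ. Follow-up after response is uniform from a to b months. Both m and the window are varied.

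**Formulas.**
- Share censored: c = (e^(−λa) − e^(−λb)) / (λ(b − a)).
- Mean of observed times, counting censored times as durations: (1 − c)/λ.
- Mean of completed responses only: ((1 − c)/λ − K)/(1 − c), where K = [(a/λ + 1/λ²)e^(−λa) − (b/λ + 1/λ²)e^(−λb)]/(b − a).

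**Worked case, m = 18, window 3 to 21.** λ = 0.03851 and 1/λ = 25.97. c = (0.8909 − 0.4455)/0.6931 = 0.643. Mean of observed times = 0.357 × 25.97 = 9.3. K = 7.05, so the mean of completed responses = (9.28 − 7.05)/0.357 = 6.2. The true mean is 26.0.

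**Step 1: fix follow-up, vary durability (months).**

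| Follow-up | True median | True mean | Censored | Mean, observed times | Mean, completed only |
|---|---|---|---|---|---|
| 3–21 | 18 | 26.0 | 64% | 9.3 | 6.2 |
| 3–21 | 30 | 43.3 | 76% | 10.2 | 6.6 |
| 3–21 | 48 | 69.2 | 84% | 10.9 | 6.8 |
| 6–24 | 12 | 17.3 | 44% | 9.7 | 6.7 |
| 6–24 | 60 | 86.6 | 84% | 13.6 | 8.0 |
| 24–60 | 18 | 26.0 | 21% | 20.4 | 15.6 |
| 24–60 | 48 | 69.2 | 55% | 31.1 | 19.5 |

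In the 3–21 window, 2.7 times the durability (48/18) raises the mean of observed times by 17%. In the 6–24 window, 5 times the durability raises it by 41%, or by 19% for completed responses only. In the 24–60 window, 2.7 times the durability raises it by 52%.

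**Step 2: fix durability at a true median of 36 (true mean 51.9), vary follow-up.**

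| Follow-up | Censored | Mean, observed times | Mean, completed only |
|---|---|---|---|
| 3–15 | 84% | 8.2 | 4.9 |
| 6–24 | 75% | 12.8 | 7.8 |
| 12–36 | 64% | 18.9 | 11.7 |
| 24–48 | 50% | 25.7 | 16.2 |

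Follow-up alone moves the figure about threefold (25.7/8.2 = 3.1), and it never exceeds half the true mean. Simulation with 33 responders and 3,000 runs per scenario agrees with the formulas to within about 0.1 month for the 6–24 window and for Step 2.

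**Step 3: a generous reading of the mean.** If it is taken as the area under the Kaplan-Meier curve up to the last event, the four windows of Step 2 give 8.3, 13.8, 20.4 and 26.4. The problem remains.

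**Step 4: the Kaplan-Meier median in the same simulations.** With a true median of 12, the typical estimate is 12.0 in every window (reached in 64%, 96%, 100% and 100% of runs for 3–15, 6–24, 12–36 and 24–48). With a true median of 24, it is 24.3 at 12–36 (reached in 82%) and 23.7 at 24–48 (99%). With a true median of 36, it is 36.2 at 24–48 (75%). With a true median of 36 and 6–24 months of follow-up, it is reached in only 14% of runs. Those runs give too short a value, but the other 86% correctly report that the median was not reached.

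**The case against.** The strongest reply is that this matters less than it seems. DOR is one of several secondary endpoints, no decision rule uses it, and the only hypothesis test is on ORR. Efficacy endpoints will be listed, so the dates survive and the SAP could still analyse them properly. That limits the damage, but it does not make the stated method right. A SAP that follows the protocol would inherit it.

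A second reply is that the 3–21 month window is short for a study expected to last about 7 years. This is fair. With longer follow-up the mean does respond to durability: with a true median of 12 months and 24 to 48 months of follow-up, about 14% are censored and the mean is 15.0 against 17.3. The statement that the figure reflects follow-up more than durability is strongest under heavy censoring. Yet the 24–60 window still gives 31.1 against 69.2 when responses are long, which is the outcome the trial hopes for.

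Third, the listed censoring rules are worded for subjects alive at study end, and the next sentence on censoring names only OS and PFS. They may never have been meant for DOR. That removes any claim of a direct contradiction, but it leaves DOR with no censoring rule at all.

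Finally, the conditional wording in brackets softens the commitment without offering a substitute.

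**Conclusion.** The concern holds: the method is wrong as written. Section 8.7 assigns an uncensored summary to a right-censored endpoint, and no other section repairs it. The direction of the bias, downward, follows whenever any responder is still in response at the cutoff. Its size depends on durability and follow-up, neither of which the protocol gives. Under exponential DOR, the mean of observed times ranged from 16% of the true mean (10.9/69.2; 84% censored) to 87% (15.0/17.3; about 14% censored) in the scenarios above.

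The primary ORR analysis is untouched. Time to response is also unaffected, because among responders it is fully observed and a mean is acceptable there.

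**What to change.** In Section 8.7, move DOR from the mean and standard error group to the Kaplan-Meier group, reporting quartiles with 95% confidence intervals among confirmed responders. Event-free rates at fixed times such as 12 and 24 months are a useful option for a cutoff at which the median is not reached.

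Add a censoring rule specific to DOR, for example at the last evaluable response assessment. Last contact does not suit, because contact can continue after response assessments have stopped.

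While the sentence is open, reconcile the end event: Section 2 counts loss of response and Section 8.7 does not. That is a separate point, but the Kaplan-Meier estimate needs one definition. Median and range for time to response would be tidy but are not required.

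The cost is a sentence or two of protocol text, carried into the SAP. No added visits, data collection or sample size.

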	exposure range of bezuclastinib in subjects with AdvSM	
from baseline in laboratory results) and dose modifications
 
 Pharmacokinetics (PK) and pharmacodynamic assessments Overall response rate (ORR) based on the modified IWG-MRT-ECNM response criteria per Central Response Review Committee (CRRC)
Part 2 Stage 1: Dose Confirmation		
Primary	To confirm the optimal dose of bezuclastinib in subjects with AdvSM	
 Safety assessments (incidence of AEs, SAEs, changes from baseline in laboratory results) and dose modifications PK and pharmacodynamic assessments ORR based on the modified IWG-MRT-ECNM response criteria per CRRC
Part 2 Stage 2: Expansion		
Primary	To determine the efficacy of bezuclastinib at the selected optimal dose in subjects with AdvSM who are evaluable based on the modified IWG-MRT-ECNM response criteria	ORR defined as the percentage of subjects classified as confirmed responders (complete response [CR], CR with incomplete hematologic recovery [CRh], partial response [PR], and clinical improvement [CI]) according to modified IWG-MRT-ECNM response criteria as assessed by CRRC
Part 1 and Part 2		
Secondary	To characterize the safety and tolerability of bezuclastinib in subjects with AdvSM	Incidence of AEs, SAEs, AEs leading to dose modifications, and changes from baseline in laboratory results
	To evaluate additional efficacy parameters with bezuclastinib in subjects with AdvSM	Duration of response (DOR), defined as the date of the first documented response (CR, CRh, PR, or CI) to date of first documented disease progression or loss of response, or death from any cause, whichever occurs first, based on modified IWG-MRT-ECNM response criteria
		Time to response (TTR), defined as the date of randomization/first dose of study drug to the date of the first documented response (CR, CRh, PR, or CI) based on modified IWG-MRT-ECNM response criteria
		Progression-free survival (PFS), defined as the date of randomization/first dose of study drug to the date of first documented disease progression, or death from any cause, whichever occurs first

		Overall survival (OS), defined as the date of randomization/first dose of study drug to the date of death from any cause
		Pure Pathologic Response (PPR), including complete remission, complete remission with partial hematologic recovery, molecular complete remission, and partial remission (Gotlib et al, 2020)

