		of first documented disease progression, or death from any cause, whichever occurs first
		Overall survival (OS), defined as the date of randomization/first dose of study drug to the date of death from any cause
		Pure Pathologic Response (PPR), including complete remission, complete remission with partial hematologic recovery, molecular complete remission, and partial remission (Gotlib et al, 2020)
		Changes in spleen and liver size assessed by magnetic resonance imaging (MRI)
	To determine the effects of bezuclastinib on serum tryptase	Changes in the levels of serum tryptase
	To determine the effects of bezuclastinib on KIT D816V mutation allele burden	Changes in the levels of KIT D816V mutation allele burden in blood and bone marrow
	To evaluate histopathologic response in the blood and bone marrow	Change in pathologic findings in the blood and bone marrow, including mast cell infiltration, monocytosis, and eosinophilia
	To assess the PK of bezuclastinib in subjects with AdvSM	Plasma concentrations and PK parameters (eg, area under the plasma concentration-time curve [AUC] and maximum observed plasma concentration [C _{max}]) of bezuclastinib
	To assess patient-reported outcomes in subjects with AdvSM	Patient Global Impression of Change (PGIC) scale and change and percent change from baseline in the following patient-reported outcome measures: Patient Global Impression of Severity (PGIS) scale, Mastocytosis Quality of Life Questionnaire (MC-QoL), and Mastocytosis Activity Score (MAS) where appropriate translations are available (Siebenhaar et al, 2018; Siebenhaar et al, 2016)
	To explore the effect of bezuclastinib in subjects with AdvSM who are non-evaluable based on the modified IWG-MRT-ECNM response criteria	
 • Incidence of AEs, SAEs, AEs leading to dose modifications, and changes from baseline in laboratory results • PPR, including complete remission, complete remission with partial hematologic recovery, molecular complete remission, and partial remission (Gotlib et al, 2020)

Objectives and Endpoints:		
	Objectives	Endpoints
Exploratory	To explore various pharmacodynamic markers and their relationship with clinical safety and efficacy	Blood and bone marrow obtained at various timepoints throughout the trial to determine the effects of bezuclastinib on pharmacodynamic markers, including KIT D816V mutation allele burden and myeloid mutation profile as a measure of pharmacodynamic activity

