4.3. SUBJECT WITHDRAWAL CRITERIA

4.3.1. Treatment Discontinuation for Individual Subjects

Treatment discontinuation is defined as an instance in which a subject permanently stops receiving study drug and does not restart drug. Subjects who experience a TEAE that is assessed as at least possibly related to study drug and require a dose interruption of more than 28 days must permanently discontinue treatment with bezuclastinib. A subject should be discontinued from study treatment if, in the opinion of the Investigator or Sponsor, it is medically necessary to do so, or if it is the wish of the subject. A subject who becomes eligible for hematopoietic stem cell transplantation (HSCT) and for whom HSCT is the most appropriate therapeutic option should discontinue treatment and receive HSCT at the discretion of the Investigator.

A subject must discontinue study treatment for:

- Protocol-specified documented disease progression
- Investigator decision
- Subject withdrawal of consent
- Development of an AE, that in the opinion of the Investigator, would render continued participation harmful to the subject
- Subject pregnancy
- Lost to follow up (ie, inability by the Investigator to contact and/or effectively monitor the subject)
- Termination of study by Sponsor
- Enrollment in another therapeutic study
- Receiving a non-protocol-approved treatment plan for treatment of the subject's AdvSM

The Sponsor is to be immediately notified if a subject discontinues study treatment for any reason. The reason for treatment discontinuation must be documented on the appropriate electronic case report form (eCRF). Noncompliance with the protocol medication/treatments and/or required follow-up, as judged by the Investigator, may result in discontinuation of study drug.

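### A survivor whose documented progression is never confirmed is carried as progression-free in the Section 8.7 PFS analysis

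*Protocol*

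**What the plan says.** **Event definition.** In Protocol Section 8.7, PFS runs to "first documented confirmed disease progression or death from any cause, whichever occurs first". The synopsis objectives table has "date of first documented disease progression, or death from any cause, whichever occurs first", and Section 2 agrees with the synopsis ("of first documented disease progression, or death from any cause, whichever occurs first"). Section 8.7 bases PFS on the modified IWG-MRT-ECNM criteria, which are set out in Appendix D.

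**Censoring.** Section 8.7 introduces its rules with "The following censoring rules will apply to subjects who survive at the end of the study". The first rule is "All subjects will be censored at the last date of study participation". The second is "Subjects who are lost to follow-up and subjects who discontinued study for any reason will be censored at the last date of contact". It then adds: "An assessment of OS and PFS will be performed with and without censoring for subsequent therapy". No rule ties PFS censoring to the last disease assessment.

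**Confirmation.** Appendix D requires progressive disease to last at least 4 weeks. One of its footnotes also counts transformation of a chronic myeloid neoplasm to AML as progression and gives no duration for it. Section 6.15.1 calls for a repeat marrow at least 4 weeks after progression but makes it optional for subjects progressing to AML or MCL.

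**After treatment stops.** Table 3 ends at the end-of-treatment visit. From then on Table 1 has one Safety Follow-up visit, 30 days (± 7) after the last dose, and contacts every 3 months for survival and disease status. Section 6.15.6 sets survival follow-up at 2 years or more. Section 5.7.1 lets a subject who starts another therapy remain in follow-up.

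**The concern.** When a PFS event must be confirmed, the plan has to say what becomes of a progression that was recorded but not confirmed. Section 8.7 answers this by default. If the subject is alive there is no event, and the time at risk continues to the last participation or contact. A subject who has progressed, stopped the drug and moved to another treatment can then add progression-free time although no response assessment is scheduled any more.

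The error has one direction: it can only lengthen PFS. Stage 2 is a single-arm expansion, so no concurrent arm carries the same error to offset it. What is at stake is the credibility of a secondary descriptive endpoint, not the trial's conclusion on response.

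**Working it through.** The protocol states no PFS event count, median or power, so there is no figure of the plan's own to reproduce. The check compares the texts and then applies simple Kaplan-Meier arithmetic.

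**Step 1: do the two event definitions differ in practice?** Mostly not. Under Appendix D a worsening that has not lasted 4 weeks is not progressive disease, so the objectives' wording contains a persistence requirement too. The clear exception is AML transformation, which Appendix D counts with no stated duration and which Section 6.15.1 does not require to be re-biopsied. Section 6.15.1 treats progression to MCL in the same way. Section 8.7 exempts neither from its confirmed qualifier.

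**Step 2: can a progression remain unconfirmed?** Yes, although several routes to confirmation exist.
- The end-of-treatment visit falls within 7 days of the decision to stop (Table 1, note c). If that decision follows the initial worsening, the visit comes before the 4-week minimum.
- Safety Follow-up laboratory tests fall on days 30 − 7 = 23 to 30 + 7 = 37 after the last dose. If the initial worsening and the last dose coincide, days 28 to 37 satisfy 4 weeks, which is 10 of the 15 possible days. Laboratory-based progression can therefore often be confirmed there.
- The Section 6.15.1 repeat marrow and clinically indicated imaging can confirm others.
- A subject who switches therapy, enters another study (a withdrawal reason in Section 4.3.2) or transforms to AML or MCL may have none of these.

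**Step 3: what does Section 8.7 do with that subject?**

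| Subject with unconfirmed progression | PFS handling under 8.7 |
|---|---|
| Dies | Event, at the later date of death |
| Alive, no censoring for subsequent therapy | Censored at last participation or contact |
| Alive, censored for subsequent therapy | Censored at the new therapy |

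In neither row for a living subject is the progression an event.

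**Step 4: size per subject.** With no censoring before the landmark, Kaplan-Meier PFS = 1 − events/n, so removing one event adds 1/n.
- Stage 2, n = 55: 1/55 = 1.8 points.
- Stage 1 arm, n = 10: 1/10 = 10 points.
- Assumed range of 1 to 5 subjects of 55: 1.8 to 5/55 = 9.1 points.

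**Step 5: does censoring at new therapy remove it?** Illustration, with every input assumed: n = 55, events evenly spaced over months 1 to 11, a 12-month landmark, and k progressors censored 1 month after progression instead of counted. The figures are averages over which k subjects are affected.

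| Events | True 12-month PFS | k = 1 | k = 5 |
|---|---|---|---|
| 11 | 44/55 = 80.0% | +1.7 points | +8.6 points |
| 20 | 35/55 = 63.6% | +1.5 points | +7.8 points |

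Earlier censoring trims the bias only slightly, because the event is still missing.

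**The case against.** The strongest reply has four parts.

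1. *The definitions coincide through Appendix D.* This largely stands. A reader might infer that one added word in Section 8.7 creates two quite different PFS endpoints, and the 4-week duration rule does not support that. It does not help with AML transformation, or with subjects lost to reassessment before 4 weeks.

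2. *Treatment continues to confirmed progression, so few subjects stop early.* Sections 3.1.2 and 3.1.3 do say this. A reader might set Section 4.3.1 ("Protocol-specified documented disease progression") against them and infer that the protocol forces a stop before confirmation. That is not supported: progression as the protocol specifies it can be read as Appendix D progression, with its 4 weeks. The difference in stopping language is editorial and forms no part of this point. Subjects can still stop earlier, by investigator decision or by switching therapy.

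3. *Confirmation is a sound choice.* This stands. Appendix D requires progression to be disease-related, Appendix F asks that drug toxicity be excluded first, and Section 1.4 lists hematological toxicity as a potential risk. Transient cytopenias could mimic progression. This argues for keeping confirmation in the main analysis, with a sensitivity analysis beside it.

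4. *The statistical analysis plan will handle it.* Section 8.1 does leave data handling to that plan. But the protocol is not silent here. It fixes the event and the censoring rules, and following them as written gives the result in Step 3.

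**Conclusion.** The point holds as a minor one. As written, Section 8.7 carries a living subject with a documented but never confirmed progression as progression-free, and the two subsequent-therapy analyses differ only in when that subject is censored. The bias is upward.

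Its total size cannot be estimated from the protocol, which gives no rate of unconfirmed progression. The 1.8 points per subject in Stage 2 assumes that the subject is carried past the landmark and that nobody is censored earlier. The range of 1 to 5 subjects is an assumption.

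A reader might infer that each affected subject adds 2 years or more of false progression-free time. That is possible for a long survivor who stays in follow-up, but it is not typical: death ends it, withdrawal to another study shortens it, and one of the planned analyses cuts it at new therapy.

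Nor does the point reach further than PFS. The primary ORR test does not use this rule, and the duration-of-response bullet in Section 8.7 does not carry the confirmed qualifier.

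**What to change.** - Use one PFS definition in the synopsis, Section 2 and Section 8.7: progression per Appendix D, dated at first documentation, or death. State that transformation to AML or MCL counts without a repeat marrow.
- Add one PFS sensitivity analysis in Section 8.7. Documented progression followed by permanent discontinuation or new anticancer therapy before confirmation is an event at the date first documented.

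The cost is wording in three places and one extra analysis, with no new visits or procedures. The downside is that a few worsenings that would not have been confirmed, such as transient drug-related cytopenias, count as events in the sensitivity analysis. Reporting it beside the main analysis shows how far PFS depends on confirmation.
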